### 6.2 Method of Assignment/Randomization (if applicable)

Randomization will take place at the individual level. Participants will be randomized to treatment as usual (regular FCS) or treatment as usual with peer support using a 1:1 allocation ratio. The randomization scheme will be generated by the study statistician and given to the data manager for implementation using the Research Electronic Data Captures (REDCap's) randomization module to maintain allocation concealment. The randomization will be stratified by gender and carried out using random permuted block sizes of 2,4, and 6. Participants will be randomly allocated after completion of the baseline assessment.

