# **7 Statistical Design**

## **7.1 Sample Size Considerations**

The primary outcome of interest is financial well-being. The primary hypothesis is that participants randomized to receive financial coaching plus peer support will have better financial well-being at 6-months compared to those who do not receive peer support. Based on prior research with low-income populations using financial well-being measures, we expect to observe a standardized effect size of 0.5. With 90% power and a two-sided type I error rate of 0.05, using a two-sample t-test (conservative), we will need 86 participants per arm (172 total) to detect the 0.5 standardized effect size. To account for a 15% missing data rate at the 6-month time point, we plan to randomize 204 participants (102 per group). For secondary outcomes at 6- and 12-months (e.g., employment, sense of belonging, social support, housing), we hypothesize that those receiving financial coaching plus peer support will perform better. Based on an effective sample size of 172 (at 6-months) and assuming an additional 10% missing data at 12-months (n=154), assuming a two-sided type I error rate of 0.01 (conservative to account for multiple testing), we will have 80% power to detect standardized effect sizes 0.53 and 0.56 for 6- and 12-months, respectively, for continuous outcomes, and absolute differences ranging from 23%-26% and 25%-27% for

6- and 12-months, respectively, for binary outcomes, for baseline rates in the treatment as usual group ranging from 20%-50%.

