## 7.2 Planned Analyses

**Analysis:** All analyses will be performed according to intent-to-treat with an overall type I error rate of 5% (two- sided) using SAS (S, N) and (Project). All analyses will follow the design and account for stratification by gender. Parametric distributional assumptions (e.g., normality) will be checked and other distributions will be considered prior to transformations and non-parametric methods. Baseline descriptive statistics (e.g., means, standard deviations, frequencies, proportions) will be presented overall and by treatment group. No inferential statistics will be presented. Baseline variables that appear to be different between the two treatment groups will be adjusted for in sensitivity analyses. Linear mixed models utilizing all data (baseline, 6- and 12-month) adjusting for gender will be used to analyze the primary outcome. We will test the time by treatment group interaction term at the 10% level of significance. If this term is significant, we will utilize a contrast term at 6-months to test the primary hypothesis. If this term is not significant, we will use the time-averaged treatment difference to test the primary hypothesis. Generalized linear mixed models (e.g., log link for binary outcomes; identity link for continuous outcomes) adjusting gender will be used to analyze secondary outcomes. Like the primary outcome, we will test for treatment by time interactions at the 0.10 level. If significant we will use contrast at 6- and 12-months to assess for differences; if there is no interaction, then a time-averaged approach will be utilized, and we will have more power to detect the proposed effect sizes. To control for false discovery for secondary outcomes, we will use the Benjamini and Hochberg method. We will make attempts to limit the amount of missing data through stipend payments to participants, but we expect that we will encounter missing data. We will employ mixed models approaches, which utilize all available data and assume missing at random. We plan to assess the robustness of our results under a missing not at random assumption using pattern mixture models. We will also consider utilizing inverse probability weighting to account for missing data, if necessary. Exploratory analyses will focus on mediation analyses and explore tests of both the direct effect of treatment on the mediator and the indirect effect as well as the mediated effects of factors in between primary and secondary outcomes as predicted in the model (see Figure 2).

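### A 10% interaction pre-test decides whether the primary test is the 6-month contrast or a time average, so the data choose the estimand and the 5% level is not kept

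*Protocol*

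**What the plan says.** Section 7.1 names financial well-being as the primary outcome and hypothesises that participants given peer support "will have better financial well-being at 6-months compared to those who do not receive peer support". The sample size is for that comparison: "using a two-sample t-test (conservative), we will need 86 participants per arm (172 total) to detect the 0.5 standardized effect size", raised to 204 for 15% missing data at 6 months.

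Section 7.2 requires the analyses to be "performed according to intent-to-treat with an overall type I error rate of 5" per cent, two-sided. On the model it says: "Linear mixed models utilizing all data (baseline, 6- and 12-month) adjusting for gender will be used to analyze the primary outcome". The decision rule follows: "We will test the time by treatment group interaction term at the 10% level of significance". If the term is significant, the 6-month contrast tests the primary hypothesis. Otherwise: "If this term is not significant, we will use the time-averaged treatment difference to test the primary hypothesis". Section 7.3 repeats the rule. Secondary outcomes follow a similar rule, and for them the protocol says that without an interaction "then a time-averaged approach will be utilized, and we will have more power to detect the proposed effect sizes".

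On timing of allocation, section 6.2 says: "Participants will be randomly allocated after completion of the baseline assessment".

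**The concern.** There are three faults.

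1. **The estimand is not fixed.** A 6-month difference and a time-averaged difference are different quantities. The rule lets the observed data pick which one tests a hypothesis worded for 6 months, and the choice has to wait for the 12-month visit. When the average is used, a 12-month effect can support a claim about 6 months.
2. **The error rate is not the one promised.** Each branch is tested at 5% on the data that chose the branch, with no adjustment.
3. **A non-significant interaction does not show a constant effect.** The pre-test can simply miss a difference between visits. There is a further problem if baseline is one of the time points, which is the literal reading of the model sentence. Allocation follows baseline, so the expected baseline difference is zero and any real effect is itself a time-by-treatment interaction. The text does not say which visits the average covers.

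The first two faults hold whether or not baseline is included. At stake is the trial's single primary claim: a positive result may not concern 6 months.

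**Working it through.** **Inputs from the protocol.** Effect 0.5 SD, two-sided 0.05, 90% power, 1:1 allocation, 86 evaluable per arm, pre-test at 10%.

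**Assumptions, because the protocol does not give them.** Within-person correlation ρ from 0.3 to 0.7; compound symmetry or AR(1); SD 1 at every visit; 86 per arm at every visit; the 6-month contrast is the arm difference at 6 months.

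**Step 1: the stated sample size.** The exact two-sample t-test needs 85.03, so 86 per arm, with power 90.3%. 86/0.85 = 101.2, so 102 per arm and 204 in total. The plan's figures reproduce. In the normal approximation used below, SE = √(2/86) = 0.1525, 0.5/0.1525 = 3.28, and power = Φ(3.28 − 1.96) = 90.6%.

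**Step 2: one case in full.** Take the time factor as 6 and 12 months only, with ρ = 0.5.

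- SE of the 6-versus-12-month difference in effect: 0.1525 × √(2(1 − ρ)) = 0.1525.
- SE of the average: 0.1525 × √((1 + ρ)/2) = 0.1321.
- With equal variances these two statistics are independent, so P(reject) = P(pre-test not significant) × P(average rejects) + P(pre-test significant) × P(6-month contrast rejects, given a significant pre-test). The last factor comes from simulation.

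| True effect at 6 / 12 months | Pre-test significant | Average rejects | 6-month contrast rejects, given significant pre-test | Whole rule |
|---|---|---|---|---|
| 0 / 0 | 10.0% | 5.0% | 14.7% | 0.900 × 0.050 + 0.100 × 0.147 = 6.0% |
| 0 / 0.3 | 62.7% | 20.6% | 4.5% | 0.373 × 0.206 + 0.627 × 0.045 = 10.5% |
| 0.5 / 0.5 | 10.0% | 96.6% | 81.2% | 0.900 × 0.966 + 0.100 × 0.812 = 95.1% |

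In the first row the excess comes from the significant branch: given a significant pre-test, the nominal 5% test of the 6-month contrast rejects in 14.7% of trials. In the second row it comes from the fallback: the average carries 0.15 SD although the 6-month effect is zero.

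**Step 3: all readings.** The whole rule was simulated with 1,000,000 draws per scenario. Reading A has baseline in the pre-test and in the average; B has baseline in the pre-test only; C uses 6 and 12 months only. The pre-test has 2 df with baseline and 1 df without.

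| Scenario (6 / 12 months) | A | B | C | Fixed 6-month contrast |
|---|---|---|---|---|
| 0 / 0 | 5.5–6.4% | 5.4–5.8% | 5.6–6.4% | 5.0% |
| 0 / 0.3 | 6.1–12.0% | 6.5–13.0% | 7.1–13.9% | 5.0% |
| 0.5 / 0.5 | 90.5–91.5% | 90.7–92.6% | 93.6–96.2% | 90.6% |
| 0.3 / 0.15 | 45–48% | 49–51% | 47–53% | 50% |

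At 0.5 fading to 0.25 SD, power is 88.0–91.1% over all readings. In the second row the lowest values belong to ρ = 0.7. A check with raw data and an estimated unstructured covariance (100,000 trials per scenario) gave 5.4–6.4%, 6.0–13.9% and 90.3–96.1% for the first three rows.

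**Step 4: how often the average is used.** With no effect, the average is used in 90% of trials on every reading. At a constant 0.5 SD it is used in 90% under C, but in only 0.2–15.5% under A. With 0.3 SD at 12 months only, reading A still uses it in 16–54%.

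**Step 5: which visits are averaged.** If baseline is included, a constant 0.5 SD becomes (0 + 0.5 + 0.5)/3 = 0.33 SD in the fallback test. The protocol's statement about more power was checked at its own secondary setting (0.53 SD, α = 0.01, compound symmetry, ρ = 0.3/0.5/0.7). The 6-month contrast has 81.6%. The average over 6 and 12 months has 95.9/92.5/88.4%, so the statement is true. The average including baseline has 72.5/60.3/50.6%, so it is false.

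**The case against.** The rule is written down in advance, so no analyst discretion enters. With no effect at all the excess is only 0.4 to 1.4 points. The larger figures need a scenario the protocol does not describe, with no effect at 6 months and 0.3 SD at 12; there peer support does work, only later, so the error concerns timing rather than benefit. The baseline argument depends on a reading that the protocol's secondary-outcome text tends to contradict: it names contrasts at 6 and 12 months and expects the average to gain power, which is true only of a post-baseline average. Even on the baseline reading, power at the design effect is not hurt. The calculations also take 86 per arm at every visit, whereas section 7.1 expects 154 in total at 12 months.

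Much of this stands as a limit on size. The excess under no effect is modest, the late-effect scenario is an illustration, and the dilution to 0.33 SD is conditional on the reading. Allowing for attrition moves the error rates by less than 1 point. None of it answers the main point. Pre-specifying a data-driven choice does not fix the estimand, and the hypothesis under test is expressly about 6 months. Nor is this a detail left to an SAP: the protocol states the rule in full, twice.

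**Conclusion.** The concern holds and should be fixed before analysis. The estimand mismatch follows from the text and needs no simulation. The promised 5% is exceeded in every scenario and reading examined where the 6-month null is true: modestly with no effect at any visit (about 5.4–6.4%), and by more when the effect appears only at 12 months (about 6–14% for 0.3 SD, falling as the correlation rises). These figures rest on the assumed correlations, the assumed 12-month effect and complete data at 86 per arm. The sample size is correct, and loss of power is not the main harm.

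**What to change.** - **Primary outcome (sections 7.2 and 7.3).** Delete the interaction pre-test. State that the single primary test is the 6-month treatment contrast from the mixed model at two-sided 5%, always reported and adjusted for the randomisation strata. The stratifier must first be reconciled: sections 6.2 and 7.2 give gender, 7.3 gives inmate status, and 7.4 adds community supervision status.
- **Baseline (optional).** Enter baseline financial well-being as a covariate or constrain the arms to a common baseline mean. This is not needed for the 5% level. It raises power at 0.5 SD to 93.0/96.6/99.6% at correlation 0.3/0.5/0.7.
- **12 months and averages.** Report the 12-month contrast and any average over 6 and 12 months as secondary only.
- **Secondary outcomes (advisable for consistency).** Report the 6- and 12-month contrasts without a pre-test, define any average over post-baseline visits only, and limit the statement about more power to such an average under a constant effect.

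The cost is wording only: no new data, no new participants, and 204 stays. The one downside is that the average is no longer a route to the primary claim. If the effect is constant and the average would have covered 6 and 12 months only, power is 90.6% unadjusted instead of 93.6–96.2%. Baseline adjustment offsets much or all of that loss, depending on the correlation.

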***Peer support:***

[figure not shown]
Half of our sample, stratified by gender, will be randomized to the 'treatment plus' group, and will also be offered one-on-one peer support from a trained Recovery Support Specialist. The peer supporter will be trained in forensic peer support and the 8 dimensions of wellness to give them additional skills to assist participants in addressing SDOH challenges. [name] and peer supporters on this project have served as trainers in forensic peer support, wellness coaching around the 8 dimensions, and on peer support training and certification. These training technologies are used throughout the country in providing training to peer supporters.

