### 5.3 Eligibility Criteria

- Participants must be 1) at least 18 years of age; 2) have been released from jail or prison 24 months ago or less; 3) self-identify as having mental health challenges; 4) living or using services in the City of New Haven and 5) be interested in receiving financial guidance.
- Ineligibility Criteria for the Financial Health and Mental Health after Incarceration intervention: Persons 1) less than 18 years of age; 2) not have been released from jail or prison 24 months ago or less; 3) not self-identify as having mental health challenges; 4) living or using services in the City of New Haven and 5) be interested in receiving financial guidance.
- Service providers/bank and credit union staff participant must be 1) at least 18 years of age and 2). a financial coach or criminal justice service provider from the New Haven area will participate in training activities during the project's first year as part of our partnership with the NH-FEC and local organizations providing services to the target group. The financial coaches and criminal justice service providers are neither participants nor research staff. These are community service providers. They are providing their usual services available to anyone.

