**7.3** All analyses will be performed according to intent-to-treat with an overall type I error rate of 5% (two- sided) using SAS (Cary, NC) and R (R Project). All analyses will follow the design and account for stratification by inmate status. Parametric distributional assumptions (e.g., normality) will be checked and other distributions will be considered prior to transformations and non-parametric methods. Baseline descriptive statistics (e.g., means, standard deviations, frequencies, proportions) will be presented overall and by treatment group. No inferential statistics will be presented. Baseline variables that appear to be different between the two treatment groups will be adjusted for in sensitivity analyses. Linear mixed models utilizing all data (baseline, 6- and 12- month) adjusting for inmate status will be used to analyze the primary outcome. We will test the time by treatment group interaction term at the 10% level of significance. If this term is significant, we will utilize a contrast term at 6-months to test the primary hypothesis. If this term is not significant, we will use the time-averaged treatment difference to test the primary hypothesis. Generalized linear mixed models (e.g., log link for binary outcomes; identity link for continuous outcomes) adjusting for inmate status will be used to analyze secondary outcomes. Like the primary outcome, we will test for treatment by time interactions at the 0.10 level. If significant we will use contrast at 6- and 12- months to assess for differences; if there is no interaction, then a time-averaged approach will be utilized, and we will have more power to detect the proposed effect sizes. To control for false discovery for secondary outcomes, we will use the Benjamini and Hochberg method. We will make attempts to limit the amount of missing data through stipend payments to participants, but we expect that we will encounter missing data. We will employ mixed models approaches, which utilize all available data and assume missing at random. We plan to assess the robustness of our results under a missing not a random assumption using pattern mixture models. We will also consider utilizing inverse probability weighting to account for missing data, if necessary. Exploratory analyses will focus on mediation analyses and explore tests of both the direct effect of treatment on the mediator and the indirect effect as well as the mediated effects of factors in between primary and secondary outcomes as predicted in the model.

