## 7.4 Data Relevance

To accomplish our aims, we have designed two components of the **Financial Health and Mental Health after Incarceration** research project, involving data collection from human subjects: (1) Enrollment and data collection of participants in the intervention (n=204), including randomization of participants who will receive regular financial capability support, (2) training of existing coaches working for the New Haven Financial Empowerment Center (NHFEC) and training for service providers currently working with the target population at various points along the criminal justice trajectory, including staff of jail diversion and forensic psychiatry programs, pre-sentencing programs, public defenders, in-prison counselors, probation and parole officers, and staff of transitional housing and reentry programs, to enable them to address common financial problems that people may face, and to understand when a referral to financial coaching is possible/appropriate. We will then conduct a series of four focus groups with the trained providers (n=40).

We will utilize a parallel-group design for the randomized control trial (RCT). Randomization will take place at the individual level. Participants will be randomized to treatment as usual (regular financial capability support) or treatment as usual with peer support using a 1:1 allocation ratio. The randomization scheme will be generated by the study statistician and given to the data manager for implementation using the Research Electronic Data Capture (REDCap) randomization module to maintain allocation concealment. The randomization will be stratified by gender community supervision status and carried out using random permuted block sizes of 2,4, and 6. Participants will be randomly allocated after completion of the baseline assessment.

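### Two parallel analysis sections fix different covariates for the primary model, and the one in section 7.3 (inmate status) matches no description of the randomisation

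*Protocol*

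**What the plan says.** **Randomisation.** Three places describe it.

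- Section 4 (Peer support): "Half of our sample, stratified by gender, will be randomized to the 'treatment plus' group".
- Section 6.2: "The randomization will be stratified by gender and carried out using random permuted block sizes of 2,4, and 6".
- Section 7.4 (Data Relevance): "The randomization will be stratified by gender community supervision status and carried out using random permuted block sizes of 2,4, and 6". No word or mark joins the two factors. Reading them as gender and community supervision status is an interpretation, and a separator may have been lost when the text was extracted.

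**Analysis.** Two sections set out what is otherwise nearly the same plan.

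- Section 7.2: "All analyses will follow the design and account for stratification by gender", and for the primary model "Linear mixed models utilizing all data (baseline, 6- and 12-month) adjusting for gender will be used to analyze the primary outcome".
- Section 7.3 (no title): "All analyses will follow the design and account for stratification by inmate status", and its primary linear mixed model is described as "adjusting for inmate status will be used to analyze the primary outcome". The secondary generalized linear mixed models carry the same covariate. Gender is not mentioned.

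Neither section refers to the other or says which one governs.

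**The concern.** An analysis that is said to follow the design should carry the factors used to stratify the randomisation. Section 7.3 makes that claim and then names a factor that no account of the randomisation contains. Two things are at stake.

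1. **Efficiency and calibration.** Stratifying balances the arms on the stratum. A model that leaves the stratum out does not credit that balance, so its standard error is too wide and some power is lost.
2. **Prespecification.** The trial has a single primary hypothesis, on financial well-being at 6 months, but two written models for testing it. Unless one is withdrawn before outcomes are compared by arm, the choice can be made after seeing the results.

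**Working it through.** **Step 1. Set the sections side by side.**

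| Section | Subject | Factor named |
|---|---|---|
| 4, Peer support | Randomisation | Gender |
| 6.2 | Randomisation | Gender |
| 7.4 | Randomisation | Gender, community supervision status (connector missing) |
| 7.2 | Analysis: strata, primary model, secondary models | Gender, all three times |
| 7.3 | Analysis: strata, primary model, secondary models | Inmate status, all three times |

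The three mentions of inmate status in 7.3 replace the three mentions of gender in 7.2 one for one. The term occurs nowhere else in the protocol.

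**Step 2. Try the possible meanings of inmate status.**

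- *Currently incarcerated or not.* Section 5.3 requires that participants "have been released from jail or prison 24 months ago or less". At enrolment the variable then has one level and no coefficient can be estimated. The 7.3 model reduces to one with no stratum in it.
- *Another label for community supervision status.* The protocol does not say this. If it were so and 7.4 were right, 7.3 would omit gender and 7.2 would omit supervision status, so neither would match. If 6.2 were right, 7.3 would adjust for a factor that is not a stratum and leave out the one that is.

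Under neither meaning does 7.3 agree with any of the three descriptions of the randomisation.

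**Step 3. Check whether the sample size depends on this.** Inputs from section 7.1: standardised effect 0.5, two-sided 0.05, power 90%, two-sample t-test, 15% missing at 6 months. The exact t-test needs 85.03 per arm, rounded up to 86, with power 0.903 at 86. Then 86 / 0.85 = 101.2, rounded up to 102 per arm, or 204 in total. The protocol's figures are reproduced. They contain no covariate, so they do not change.

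**Step 4. Size the cost of omitting the stratum.** Let R² be the share of outcome variance explained by the omitted strata. The protocol gives no value, so the values below are assumptions. The 7.3 covariate is taken as unrelated to the outcome, and s = √(1 − R²).

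- Standard error overstated by the factor 1/s
- Actual two-sided type I error = 2Φ(−1.96/s)
- With 86 per arm, the standardised signal is 0.5/√(2/86) = 3.279
- Power without the stratum = Φ((3.279 − 1.96)/s)
- Power with the stratum = Φ(3.279/s − 1.96)

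| Assumed R² | SE factor | Actual type I error | Power, stratum omitted | Power, stratum included |
|---|---|---|---|---|
| 0 | 1.000 | 0.050 | 0.906 | 0.906 |
| 0.02 | 1.010 | 0.048 | 0.909 | 0.912 |
| 0.05 | 1.026 | 0.044 | 0.912 | 0.920 |
| 0.10 | 1.054 | 0.039 | 0.918 | 0.933 |

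At R² = 0.10 the power given up is 0.933 − 0.918 = 0.015. (The first row is 0.906 rather than 0.903 because these power figures use the normal approximation.)

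**The case against.** The strongest reply is that the intended factor is hardly in doubt. Gender is named in sections 4, 6.2, 7.2 and 7.4, while inmate status occurs in one section only. The table of contents goes from 7.2 Planned Analyses to 7.3 Data Relevance. In the body an untitled 7.3 has been inserted, which pushes Data Relevance to 7.4. That looks like a pasted duplicate rather than a rival plan. It is a plausible history, but 7.3 is current text, it now carries subsections 7.3.1 to 7.3.3, and the revision history records no change of strata. Nothing in the document tells a reader to disregard it.

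A second reply is that inmate status may vary among released people. Recruitment includes halfway houses and community supervision programmes, so the term could refer to supervision or custody arrangements. This weakens the one-level argument, which depends on a plain reading of an undefined term. It does not remove the mismatch, as Step 2 shows.

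A third reply concerns size, and it stands. The factor 1/√(1 − R²) is the result for a single cross-sectional outcome. The planned mixed model uses baseline, 6- and 12-month data, and a fixed characteristic such as gender explains less of the variance once baseline is taken into account. The figures are therefore better read as an upper range. The error is conservative, with no inflation of false positives from the omission itself. If inmate status is constant, the two candidate models differ by one covariate that randomisation has balanced, so their estimates should be close.

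**Conclusion.** The concern holds. Section 7.3 is wrong as written: its analyses cannot both follow the design and account for stratification by a factor that no description of the randomisation names. The protocol also states two different primary models without saying which applies, and section 7.4 gives a different set of strata from sections 4 and 6.2.

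The numerical effect is small: a standard error about 1% to 5% too wide for assumed R² between 2% and 10%, a power loss of at most 0.015 over that range, and no effect on the 204 to be randomised. These figures rest on the assumed R², on treating the 7.3 covariate as uninformative, and on a single-time-point approximation. The main reason to act is that the model for the primary hypothesis is not uniquely fixed. That conclusion rests on none of these assumptions, nor on how the missing connector in 7.4 is read.

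**What to change.** 1. Keep one analysis section and delete the duplicate, restoring the numbering in the table of contents.
2. Confirm which factor or factors were actually loaded in the REDCap randomisation module. The protocol says the scheme goes to the data manager for REDCap but does not show what was implemented.
3. Replace inmate status with exactly those factors: gender, plus community supervision status if it was implemented. If supervision status stays, define its levels and restore the missing connector.
4. Make sections 4, 6.2, 7.2 and 7.4 name the same list, and state that the primary and secondary models adjust for it.

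The cost is a wording amendment and one check with the data manager. Sample size, randomisation and data collection do not change, provided that gender and any supervision stratum are recorded at randomisation. The amendment should be in place before outcomes are analysed by arm.
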